September 26th 2021

Study Protocol and Statistical Analysis Plan

ClinicalTrials.gov Identifier: NCT04243421

Marginal Bone and Soft Tissue Alterations After Use of OsseoSpeed EV Profile Implants

Aim

Evaluation of the marginal bone and soft tissue alterations after the OsseoSpeed™ EV Profile implants placement in anterior maxilla.

Study design

A case series study. Each patient will provide only one site with sloped ridge for implantation. The trial will have a duration of 1 year.

The principles outlined in the Declaration of Helsinki on clinical research involving human subjects will be adhered to a written informed consent which will be obtained for each patient.

Inclusion criteria

- lack of tooth in position of central incisors, canines and premolars
- minimum age – 18 years

The definitive inclusion of the site will be made at surgery after final osteotomy - if the site demonstrates a lingual-buccal bone height discrepancy of 1.5-2.0 mm.

Exclusion criteria

- Smoking
- Uncontrolled diabetes
- Pregnancy or lactation
- Poor oral hygiene

Number of patients to be included

It is planned to include 30 patients in to the study.

Outcome measures

Implant survival: the reason for implant loss will be recorded.

Complications and adverse events: any complication (flap dehiscence, suppuration, etc.) and adverse events will be recorded and reported by study group by the blinded assessors.

Pink esthetic score (1) – at the temporary crown delivery, at final crown delivery, 6 months post final crown delivery

Papilla index (2) - at the temporary crown delivery, at final crown delivery, 6 months post final crown delivery

Changes in radiographic marginal bone levels and width at buccal and palatal aspects: differences between baseline (the day of surgery) and 1-year measurements on CBCT will be made.

Materials

- Implant OsseoSpeed™ EV Profile \varnothing 4.2 mm
- cover screw
- healing abutment
- temporary abutment
- temporary crown
- impression coping
- implant replica
- Atlantis abutment
- definitive full ceramic crown
- Sutures: non-resorbable 5/0 or 6.0 Ethilon (Ethicon Johnson & Johnson Company, New Brunswick, NJ, USA)

Clinical procedures

Screening visit

Potentially eligible patients are screened to establish their eligibility for the study.

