The osteotomy will be prepared with the conical drill therefore the implant will be placed in special manner - it's sloped part is located at the buccal osteotomy preparation. The buccal rim of the implant is positioned at the crestal bone level, the palatal rim may be situated either at the level of the bone crest or 0.5 mm below.

The flap will be sutured with 5/0 or 6/0 non-absorbable Ethilon sutures using the mattress and single interrupted sutures. Clinical photographs of the treated site after flap suturing have to be taken.

Post-surgical instructions and follow-up

- Ibuprofen 400 mg 2-4 times per day will be prescribed in case of pain. In case of gastric problems it will be replaced by Paracetamol 1 g (max 4 g per day).
- Patient will be reminded to go on with the antibiotic prophylactic therapy as previously described.
- Chlorhexidine mouthwash 0.12% for 1 minute twice a day for 3 weeks will be provided.
- Suture removal after 2 weeks.

Check-ups and maintenance

Appointments will be scheduled at weeks 1, 2, 4, and 6. Clinical photographs will be taken. At these time points presence of suppuration and flap dehiscence will be recorded dichotomously as presence/absence.

Uncovering procedure will be scheduled at 8 weeks post-op. After crestal incision and gentle flap elevation the height of denudated buccal implant surface (if present) will be measured using a periodontal probe. Then the hilling abutment will be screwed in and single interrupted sutures

will be placed with the use 5/0 or 6/0 non-absorbable Ethilon sutures (if necessary). Suture removal is planned 7 days after procedure. Clinical photographs will be taken.

Temporary crown will be delivered 3 months post implant placement. Clinical examination (PES, PI) will be performed. Clinical photographs will be taken. Control CBCT will be taken.

Final prosthetic reconstruction will be delivered 6 months post-op. Clinical examination (PES, PI) will be performed. Clinical photographs will be taken.

1 year evaluation

Clinical examination (PES, PI) will be performed.

Clinical photographs of the study site have to be taken.

Control CBCT will be taken.

In case of any complication observed during any of the scheduled visit or during an emergency visit, intraoral radiographs and clinical photographs have to be taken and the CRF should be filled in.

Summary of the procedures and follow-up

| | |
|---------|---|

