| Day 0 | Antibiotic coverage, preoperative clinical photographs, flap, intrasurgical measurements with definitive inclusion, treatment, post-operative photographs, CBCT |
| Week 1 | Check: suppuration, dehiscence |
| Week 2 | Check: suture removal, suppuration, dehiscence, photographs |
| Week 4 | Check: suppuration, dehiscence, photographs |
| Week 6 | Check: suppuration, dehiscence, photographs |
| Week 8 | Uncovering procedure, intrasurgical measurements, healing abutment installation, photographs |
| Month 3 | Temporary prosthetic reconstruction delivery, PES, PI, photographs, CBCT |
| Month 6 | Definitive prosthetic reconstruction delivery, PES, PI, photographs |
| 1 year | PES, PI, photographs, CBCT. |

Drop-outs

All drop-outs should be reported and the reason for dropping out should be investigated and reported per study group. No included patient can be excluded, for any reasons, by the clinical investigators.

Statistical analysis

The variables will be described by the parameters of descriptive statistics, i.e. arithmetic mean with 95% confidence interval, standard deviation, median, lower and upper quartile, as well as the minimum and maximum value.

The normality of the distribution will be tested with the Shapiro-Wilk test.

For the comparisons of 2 groups, the Student's t-test for related variables or Wilcoxon's test will be used (depending on whether the assumption of normal distribution is met).

Related variables ANOVA or Friedman's test along with Dunn's multiple comparison test with Bonferroni correction will be used to compare the 3 groups (depending on whether the assumption of normal distribution is met). Additionally, the trend analysis will be performed with the Page test or the linear trend test.

The results were considered statistically significant at $p < 0.05$.

PQStat version 1.8.0.392 will be used for statistical analyzes.

Administrative procedures and data management

Clinical record forms (CRFs) should be filled in at the time of data collection. Complete CRFs, and disks containing the digitized clinical photographs and radiographs should be attached to the study folder of each patient.

All data requested for this study will be collected using paper CRFs. The CRFs will be stored in a secure locked place to which only the principle investigator and the responsible for data collection will have access to. Patient identity will be protected and known only to the study participants listed in the present protocol.

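### Does this case series need a named primary outcome or a multiplicity rule across outcomes?

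*Combined protocol and SAP*

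**What the plan says.** The Aim covers marginal bone and soft tissue together, and Study design calls the trial a case series. Outcome measures lists implant survival, complications, PES, PI and CBCT bone measures without ranking them. The bone item reads "Changes in radiographic marginal bone levels and width at buccal and palatal aspects", and its contrast is fixed: "differences between baseline (the day of surgery) and 1-year measurements on CBCT will be made". PES and PI are each scored at three visits.

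Statistical analysis begins with description, including the "arithmetic mean with 95% confidence interval". It then gives a paired t-test or Wilcoxon test for two time points, and repeated-measures ANOVA or Friedman for three. Dunn's "multiple comparison test with Bonferroni correction will be used to compare the 3 groups". A further sentence reads: "Additionally, the trend analysis will be performed with the Page test or the linear trend test". The section closes with "The results were considered statistically significant at" p < 0.05.

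The visit table also places a CBCT at month 3 ("Temporary prosthetic reconstruction delivery, PES, PI, photographs, CBCT"), and Check-ups and maintenance says of that visit "Control CBCT will be taken".

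**The concern.** In a single-arm study the three groups can only be three time points of one variable. The Bonferroni step therefore protects the pairwise comparisons within PES or within PI, and nothing protects the set of outcomes.

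The number of tests is also open. Bone level and width at two aspects could mean four tests, two or one. The trend test may or may not carry a significance claim. The month-3 scan would allow a three-time bone analysis beside the day 0 to 1 year contrast.

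With one publication planned, the worry is that whichever result falls below 0.05 becomes the headline, and that this happens by chance well above one time in twenty.

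**Working it through.** The plan states no family-wise error rate, power or sample-size derivation, so there is no figure of its own to reproduce.

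**Inputs from the documents.** 30 patients; 0.05 per test; bone compared at two times; PES and PI at three visits.

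**Assumptions.** Two-sided tests; a common correlation between outcomes from 0 to 0.9; in the simulations with a Friedman and Page branch, PES and PI rounded to assumed scales of 0–10 and 0–4.

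**Independent tests, none with a true change.** The chance of at least one false positive in k tests is 1 − 0.95^k:
- k = 3 (one bone test, PES, PI): 1 − 0.95³ = 14.3%
- k = 6 (four bone tests, PES, PI): 1 − 0.95⁶ = 26.5%
- k = 8 (trend tests for PES and PI added): 1 − 0.95⁸ = 33.7%

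The last figure is too high, because the omnibus and trend tests use the same data. Simulated together for PES, they gave a false positive 7.2–7.5% of the time. Taking 7.5% for each of PES and PI, the eight-test value is 1 − 0.95⁴ × 0.925² = 30.3%.

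**Correlated outcomes, eight tests, simulated at n = 30:**

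| Correlation | ANOVA + linear trend | Friedman + Page |
|---|---|---|
| 0 | 30.6% | 30.4% |
| 0.5 | 25.3% | 25.3% |
| 0.7 | 20.7% | 21.2% |
| 0.9 | 14.1% | 16.5% |

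Across both branches that the plan allows, the range is about 14–31%. With three tests the simulated range is about 9.6–14.2%. A month-3 bone analysis with every trend test counted reaches about 37% at zero correlation, but Outcome measures does not define that analysis as an outcome.

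**Some outcomes truly change.** Only the unchanged outcomes can give a false positive:
- All four bone measures change: at most 1 − 0.95² = 9.8% from the PES and PI omnibus tests, or 1 − 0.925² = 14.4% with trend (simulated 8.1–9.7% and 12.0–14.4%).
- Only PES and PI change: at most 1 − 0.95⁴ = 18.5% (simulated 9.4–18.8%).

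**Cost of adjusting.** Bonferroni over eight tests uses 0.05/8 = 0.00625 and gives 1 − 0.99375⁸ = 4.9% if the tests are independent. For a paired t-test at n = 30 and a true change of 0.53 SD, power falls from 80% at 0.05 to 49% at 0.00625. Holm over three secondary bone measures starts at 0.05/3 = 0.0167, where power is 64%.

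**What is reported in any case.** The 95% interval for a mean change has half-width t(0.975, 29)/√30 = 2.045/5.477 = 0.37 SD of the change.

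**The case for a change.** The strongest case for a change is that the plan is not purely descriptive. It names hypothesis tests, a trend test and a significance threshold, and it commits to a publication. Once significance is declared, a reader should know which result answers the question. Naming a primary outcome before analysis would cost only wording and would leave that test at 0.05. The planned intervals do not remove the issue, since they are not joint either.

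Much of this stands. No outcome is ranked, no rule spans the outcomes, and each reading with at least three tests gives about twice 5% or more when nothing changes.

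It does not show that the plan goes wrong. The outcomes, their visits and the test types are all listed, so a reader can set a publication against the list; what is uncertain is a small count of tests, not an open-ended search. The bone contrast is already fixed as day 0 to 1 year, which makes the month-3 scan a scheduled image and not a defined test. A single primary outcome would leave either bone or soft tissue without formal inference although the aim names both. Two primaries, a fixed order, or treating every p-value as exploratory are equally defensible. Reasonable statisticians differ on whether a 30-patient case series needs any of these.

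**Conclusion.** The observation is accurate but calls for no change. If nothing changes, the chance of some false significant result is about 14–31% on the eight-test reading and about 10–14% with three tests, and it falls when some outcomes do change. These figures depend on assumed correlations, two-sided tests and an inferred number of tests.

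The plan claims no overall 5% rate. There is no comparator or stopping rule, and no efficacy decision hangs on a p-value. Each variable is reported with its mean and 95% interval, and each test is valid at its own level. An analyst would sensibly read the p-values as unadjusted, result by result, and the trend tests as supplementary. Neither a significant result nor a non-significant one should then be read as more than that; in particular, at a half-width of 0.37 SD, a non-significant bone change does not show stability. Adding a hierarchy or a correction is a fair trade-off between overall error control and inference on both halves of the aim, and it does not repair an error.
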